#### ***Analysis of pre-treatment and post-treatment adverse events***

- All pre-treatment AEs by primary SOC and PT, showing number (%) of patients with at least one pre-treatment AE sorted by SOC internationally agreed order and decreasing incidence of PTs within SOC.
- All pre-treatment AEs leading to treatment discontinuation by primary SOC and PT, showing number (%) of patients with at least one pre-treatment AE leading to discontinuation, sorted by SOC internationally agreed order and decreasing incidence of PTs within SOC.
- All post-treatment AEs by primary SOC and PT, showing number (%) of patients with at least one post-treatment AE sorted by SOC internationally agreed order and decreasing incidence of PTs within SOC.
- All post-treatment serious AEs by primary SOC and PT, showing number (%) of patients with at least one post-treatment serious AE sorted by SOC internationally agreed order and decreasing incidence of PTs within SOC.

In case the number of patients with at least one adverse event is very small (analyses per country or pooled countries, post-treatment AEs for example), listings might be an alternative presentation of the results.

#### ***Analysis of product complaints***

- Number (%) of patients experiencing product complaints.
- Number (%) of patients experiencing product complaints associated with a TEAE.

#### **2.4.5.2 Deaths**

The following summaries of deaths will be generated for the safety population.

- Number (%) of patients who died by study period (TEAE, on-study, post-study) summarized on the safety population.
- Treatment-emergent adverse events leading to death (death as an outcome on the AE case report form page as reported by the Investigator) by primary SOC, HLTG, HLT, and PT showing number (%) of patients sorted by internationally agreed SOC order, with HLTG, HLT, and PT presented in alphabetical order within each SOC.

#### **2.4.5.3 Analyses of laboratory variables**

The summary statistics (including mean, median, Q1, Q3, SE Min and Max) of some laboratory variables (absolute values and changes from baseline) will be calculated for each visit, last and worst value assessed during the treatment period. Since no central laboratory was used in this study, results obtained from local laboratories will be converted into the units listed in [Appendix A](#). For a given parameter, if no unit is indicated, no quantitative analysis will be performed.

The incidence of PCSA (list provided in [Appendix A](#)) at any time during the TEAE period will be summarized by biological function whatever the baseline level and/or according to the following baseline status categories:

- Normal/missing.
- Abnormal according to PCSA criterion or criteria.

For parameters for which no PCSA criteria are defined, similar table(s) using the normal range will be provided. A listing of patients with at least one post-baseline PCSA will be provided.

The absolute change in HbA1c (%) will be assessed from baseline to Weeks 12, 24, 48, 72, 96 and EOT/EOS.

For parameters HbA1c, FPG and LDL-C plots will be displayed; mean changes from baseline with the corresponding SE will be plotted over time (at same time points).

For the parameters assessed through dipstick urinalysis, no central laboratory was used. As a consequence, the results of statistical analyses on these parameters will have to be interpreted with caution.

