STATISTICAL CONSIDERATIONS	
Sample size determination: No formal sample size calculation is performed. The table below displays the 95% Confidence intervals (95%CI) associated to a variety of adverse event rates for a targeted sample size of 1300 patients.
 

Adverse event rates	10%	20%	30%	40%	50%	

95%CI	[8.4%; 11.6%]	[17.8%; 22.2%]	[27.5%; 32.5%]	[37.3%; 42.7%]	[47.3%; 52.7%]	

 
For a rare non observed event, by using the rule of three, it can be estimated that the upper limit of the 95% confidence interval of the event rate is approximately 0.23% (1 per 433).
 
Analysis population: Safety population: all enrolled patients who actually received at least one dose or partial dose of alirocumab.
 
Efficacy population: Modified Intend To Treat population (mITT): all enrolled patients who received at least one dose or partial dose of alirocumab, with a baseline LDL-C value available and with at least one on-treatment LDL-C measurement during the efficacy treatment period.
 
Primary analysis: Safety analysis (adverse events, laboratory, product complaints and vital signs) will be performed on the safety population. Only descriptive summaries will be provided. The number of adverse events (AEs) during the study will be displayed. Adverse event incidence tables will present, by system organ class (SOC) high level group term (HLGT), high level term (HLT) and preferred term (PT), the number (n) and percentage (%) of patients experiencing an AE.
 
Secondary analysis: The effects of alirocumab will be documented by the proportion of patients reaching calculated LDL-C <100 mg/dL (2.59 mmol/L) at Week 12, the proportion of patients reaching calculated LDL-C < 70 mg/dL (1.81 mmol/L) at Week 12 as well as by values and percent changes from baseline in LDL-C, non-HDL-C, total-C, HDL-C, and TG levels after 12 weeks of treatment and at other time points. A descriptive analysis of the SIAQ will be done on the safety population. More details regarding statistical analyses will be provided in the SAP.
	Adverse event rates	10%	20%	30%	40%	50%	95%CI	[8.4%; 11.6%]	[17.8%; 22.2%]	[27.5%; 32.5%]	[37.3%; 42.7%]	[47.3%; 52.7%]
Adverse event rates	10%	20%	30%	40%	50%								

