### **9.1.2 Safety laboratory**

The clinical laboratory data consist of urinalysis and blood analysis:

- Hematology (RBC count, hemoglobin, hematocrit, platelets, WBC count with differential blood count).
- Standard chemistry (fasting plasma glucose, sodium, potassium, chloride, bicarbonate, CPK, calcium, phosphorous, urea nitrogen, creatinine and calculated creatinine clearance using Cockcroft-Gault formula or eGFR using MDRD Study equation, uric acid, total protein, lactic dehydrogenase (LDH), albumin,  $\gamma$  Glutamyl Transferase [ $\gamma$ GT] Hepatitis B antigen, Hepatitis C antibody).
- HbA1c.
- Liver panel (ALT, AST, ALP, and total bilirubin).

Some additional safety laboratory parameters may be reflexively measured, based on actual data (please refer to [Section 10.4.5](#)).

Clinical laboratory values will be analyzed after conversion into standard international units. Standard international units will be used in all listings and tables.

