**11.4.2.2 Analysis of laboratory data and vital signs**

The summary statistics (including mean, median, Q1, Q3, standard error, minimum and maximum) of all laboratory variables, all vital signs parameters (raw data and changes from baseline) will be calculated for each visit, last and worst value assessed during the treatment period. For selected parameters, mean changes from baseline with the corresponding standard error will be plotted over time (at same time points).

- The incidence of PCSAs at any time during the TEAE period (on-treatment PCSAs) will be summarized whatever the baseline level and/or according to the following baseline categories:
  - Normal/missing,
  - Abnormal according to PCSA criterion or criteria.

For laboratory parameters for which PCSA criterion is not defined, similar table(s) using the normal range could be provided.

The absolute change in HbA1c (%) will be assessed from baseline to Week 12, 24, 72, 96 and EOT/EOS.

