#### **2.1.4.3 *Laboratory safety variables***

The clinical laboratory data consist of urinalysis and blood analysis.

Blood samples for laboratory tests are drawn at screening visit, Week 4 (except HbA1c), Week 8 (only for liver panel), Week 12, Week 24, Week 48, Week 72, Week 96 and EOT/EOS. Hepatitis B antigen is measured at screening only and Hepatitis C antibody at screening and at EOT/EOS. Serum pregnancy test is performed at screening and urine pregnancy test is performed at inclusion and at the end of study.

- Hematology (red blood cells [RBC] count, hemoglobin, hematocrit, platelets, white blood cells [WBC] count with differential blood count).
- Standard chemistry (fasting plasma glucose, sodium, potassium, chloride, bicarbonate, CPK, calcium, phosphorous, urea nitrogen, creatinine and calculated creatinine clearance using Cockcroft-Gault formula or Estimated Glomerular Filtration Rate [eGFR] using modification of the diet in renal disease (MDRD) Study equation, uric acid, total protein, lactic dehydrogenase (LDH), albumin,  $\gamma$ -Glutamyl Transferase [ $\gamma$ GT] Hepatitis B antigen, Hepatitis C antibody).
- HbA1c.
- Liver panel (ALT, aspartate aminotransferase [AST], alkaline phosphatase [ALP], and total bilirubin).
- Serum and urine pregnancy test.

Urinalysis - dipstick is performed at site or at the local Laboratory at screening, inclusion, Week 12, EOT/EOS visits and as needed during the study at investigator's discretion. It will assess for WBC, RBC, pH, specific gravity (qualitative/quantitative), and for the presence of blood, protein, glucose, ketones, nitrates, leukocyte esterase, uro-bilinogen and bilirubin.

Technical formulas are described in [Section 2.5.1](#).

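### The SAP narrows the protocol's laboratory summaries from all variables to some, and six scheduled chemistry tests lose their quantitative change-from-baseline summary without this being declared

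*SAP*

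**What the plan says.** Laboratory data are part of the primary analysis. The protocol's Clinical Trial Summary states: "Safety analysis (adverse events, laboratory, product complaints and vital signs) will be performed on the safety population". Protocol 9.1.2, which sits under Primary Endpoints, lists the tests and adds "Clinical laboratory values will be analyzed after conversion into standard international units", with no test excepted. Protocol 11.4.2.2 then calls for summary statistics "of all laboratory variables, all vital signs parameters (raw data and changes from baseline) will be calculated for each visit, last and worst value" during treatment.

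SAP 2.4.5.3 provides the same statistics only "of some laboratory variables (absolute values and changes from baseline) will be calculated for each visit", with last and worst value. It notes that there was no central laboratory, so "results obtained from local laboratories will be converted into the units listed in" Appendix A. It continues: "For a given parameter, if no unit is indicated, no quantitative analysis will be performed". For parameters without a PCSA criterion it commits to incidence tables against the normal range.

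The chemistry panel in SAP 2.1.4.3 includes "uric acid, total protein, lactic dehydrogenase (LDH), albumin", and also bicarbonate, calcium, phosphorus and gamma-GT. SAP 1.5, which records major changes to the protocol's statistical section, does not mention a reduced set of laboratory summaries. SAP 1.6 is marked as not applicable.

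**The concern.** In a single-arm study the change from baseline is the main internal contrast for a laboratory test. If a test has only in-range and out-of-range counts, a shift that stays within the normal range does not show.

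The selection also looks like a by-product, not a choice. Appendix A is the sponsor's list of PCSA thresholds, dated May 2014, and the first patient was enrolled on 08 July 2015. It carries criteria for lipase, amylase, CRP, orthostatic blood pressure and ECG, none of which is scheduled here, and omits six tests that are. It reads as a general threshold list, yet the unit rule lets it decide which laboratory variables are summarised quantitatively. The word *some* names no variables, so even tests that do have a unit are not firmly pre-specified. SAP 2.4.5.4 keeps *all* for vital signs, so only the laboratory half of the protocol's sentence was cut back.

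**Working it through.** The documents give no figure on this point, so the check is a comparison of lists.

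**Inputs.** Scheduled tests: Protocol 1.2 (flow chart footnotes c, d and f), Protocol 9.1.2 and SAP 2.1.4.3. Rows and units: SAP Appendix A. Only blood tests with a numerical result are counted; hepatitis serology, pregnancy tests and dipstick urinalysis are left out. Creatinine clearance and eGFR are counted separately, and the differential white count as five parameters.

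| Panel | Parameters | In Appendix A with a unit or ULN scale | Absent |
|---|---|---|---|
| Standard chemistry | 17 | 11 | 6 |
| Liver panel | 4 | 4 | 0 |
| HbA1c | 1 | 1 | 0 |
| Hematology | 10 | 10 | 0 |
| Total | 32 | 26 | 6 |

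The 11 chemistry parameters present are glucose, sodium, potassium, chloride, CPK, urea nitrogen, creatinine, creatinine clearance, eGFR, uric acid and albumin. The six absent are bicarbonate, calcium, phosphorus, total protein, LDH and gamma-GT.

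**What the six keep and lose**
- Mean, median, quartiles and change from baseline by visit: required by Protocol 11.4.2.2, excluded by the unit rule in SAP 2.4.5.3.
- Last and worst value: the same.
- PCSA incidence: none, because there is no criterion.
- Normal-range incidence tables: retained.

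**Sensitivity of the count.** Six assumes that multiples of the upper limit of normal (ULN) count as an indicated unit. If they do not, CPK, ALT, AST, alkaline phosphatase and total bilirubin drop out too, giving 6 + 5 = 11.

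**Precision of what is dropped (illustration on assumed inputs).** The documents give no standard deviations, within-patient correlations or relevant shifts for these tests. Assume a mean shift of 0.1 SD, a correlation ρ between baseline and follow-up of 0 to 0.5, and n of 1100 (initially planned) to 1300 (current target), all contributing.

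SE of the mean change, in SD units = √(2(1−ρ)) / √n

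- ρ = 0.5, n = 1300: 1/√1300 = 0.028, so 0.1 SD is 3.6 SE.
- ρ = 0.5, n = 1100: 1/√1100 = 0.030, so 3.3 SE.
- ρ = 0, n = 1300: 1.414/√1300 = 0.039, so 2.5 SE.
- ρ = 0, n = 1100: 1.414/√1100 = 0.043, so 2.3 SE.

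On these inputs the shift is about 2.3 to 3.6 SE. Full n is optimistic after Week 12, since SAP 1.1 expects very variable numbers from then on. The illustration does not model the retained tables, which count any abnormality over the treatment-emergent period.

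**The case against.** Several points on the other side stand.

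- **The six tests are not left unanalysed.** A reader might infer that nothing remains, or no comparison with baseline of any kind. SAP 2.4.5.3 does not support that: the normal-range tables may be split by baseline status. The SAP is firmer here than Protocol 11.4.2.2, which says only that such tables could be provided. Abnormalities that are symptomatic, need treatment or consultation, alter dosing or are serious also reach the adverse event tables through Protocol 10.4.2.
- **The six are not the headline laboratory parameters.** A reader might infer that the core of the primary safety assessment is lost. The short list in Protocol 9.1 names none of the six, and every test it does name has an Appendix A row. The six are nevertheless listed in 9.1.2 under the same Primary Endpoints heading, and 11.4.2.2 makes no distinction.
- **The SAP may revise the protocol.** Protocol 11 makes its text the basis for a plan that can be changed before database lock, and whether this change is major enough for SAP 1.5 is a judgement. That permits the change, but gives no reason for it. The lack of a central laboratory does not explain it, because the same paragraph converts other local results to Appendix A units.
- **The unit rule could mean a result reported without a unit.** The preceding sentence points to Appendix A, which makes that the natural reference. If the other reading is intended, the sentence needs rewording.
- **A literal *all* goes too far.** It would call for means of serology, pregnancy tests and qualitative dipstick items, so some limit is needed.

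It is also tempting to say that a real drug effect would be missed. The documents give no shift of interest for these tests, and a single arm could not attribute one to treatment.

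**Conclusion.** The concern holds as an undeclared narrowing of a descriptive analysis. Six of 17 quantitative standard-chemistry parameters (six of 32 blood-test parameters) lose the quantitative change-from-baseline, last-value and worst-value summaries that the protocol promises, and they have no PCSA criterion. This rests on two readings: that an indicated unit means one given in Appendix A, and that multiples of ULN count as a unit. It does not depend on the 0.1 SD illustration. No numerical error is involved, and no hypothesis test, sample size or decision rule rests on laboratory means, so the consequence is modest. It deserves correction because the SAP states an exclusion rule against the protocol's text, for data already collected, without giving a reason for leaving these tests out.

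**What to change.** 1. In Appendix A, or in a separate unit table cited from SAP 2.4.5.3, give a reporting unit for the six tests: SI units for bicarbonate, calcium, phosphorus and total protein; multiples of ULN for LDH and gamma-GT, in line with the Appendix A rule for the other enzymes.
2. In SAP 2.4.5.3, replace *some laboratory variables* with *all quantitative laboratory variables*. This restores the protocol's scope without reaching serology, pregnancy tests or qualitative dipstick results.
3. State the direction of the worst value for the six (minimum, maximum or both), because SAP 2.4.5 takes that direction from the PCSA list.
4. If any restriction is kept, name the variables concerned, and declare and justify it in SAP 1.5.

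The cost is a few lines of SAP text, unit conversion for the six tests and six more parameters in existing descriptive tables. LDH and gamma-GT should be read cautiously because local laboratories were used. No new data collection is needed.

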### ***Drug-induced liver injury***

The liver function tests, namely AST, ALT, alkaline phosphatase, and total bilirubin, are used to assess possible drug-induced liver toxicity. The proportion of patients with PCSA values or ALT increase as defined in AESI section (see [Section 2.1.4.1](#)) at any post-baseline visit by baseline status will be displayed for each parameter.

A graph of distribution of post-baseline peak values of ALT versus peak values of total bilirubin will also be presented. Note that the ALT and total bilirubin values are presented on a logarithmic scale. The graph will be divided into 4 quadrants with a vertical line corresponding to 3 x ULN for ALT and a horizontal line corresponding to 2 x ULN for total bilirubin.

#### **2.4.5.4 Analyses of vital sign variables**

The summary statistics (including mean, median, Q1, Q3, SE, Min and Max) of all vital signs parameters (raw data and changes from baseline) will be calculated for each visit, last and worst value assessed during the treatment period.

Additionally, the incidence of PCSAs at any time during the TEAE period will be summarized irrespective of the baseline level and/or according to the following baseline status categories:

- Normal/missing.
- Abnormal according to PCSA criterion or criteria.

#### **2.4.6 Analyses of SIAQ®**

##### ***Analysis of the PRE-SIAQ***

Analysis of the PRE-SIAQ (see [Appendix B](#)) will be only descriptive and will be performed in the patients belonging to the safety population and who self-injected provided that they filled in the questionnaire before the training self-injection with placebo, and regardless of whether they completed the POST-SIAQ after the subsequent self-injections of alirocumab.

Each of the 7 items of the PRE-SIAQ will be qualitatively described (number and percentage of patients for each modality of each item). A quantitative analysis will be provided for each of the 3 domains of the PRE-SIAQ (feelings about injection, self-confidence, satisfaction with self-injection).

It will be checked that all patients who self-injected at least once during the observational period performed a training injection with placebo.

##### ***Analysis of the POST-SIAQ***

Analysis of the POST-SIAQ (see [Appendix B](#)) will also be only descriptive and will be performed in the patients of the safety population who gave themselves at least one alirocumab injection (see [Section 2.3.3](#)) regardless of whether they completed the PRE-SIAQ. A descriptive summary will be provided at Weeks 4, 8, 12, 24, 48, 72 and 96.

Each of the 27 items of the POST-SIAQ will be qualitatively described with number and percentage of patients for each modality of each item. A quantitative analysis of the scores by domains will be provided for each of the 6 domains of the POST-SIAQ (feelings about injection, self-image, self-confidence, injection-site injection, ease of use, satisfaction with self-injection).

If questionnaires were completed while the patient did not self-inject or were not performed the same day of an injection, they will not be considered for the analysis.

### ***Comparison of domain scores between PRE-SIAQ and POST-SIAQ***

Regarding the analysis of the change in the perception of self-injection between the first self-injection and the subsequent self-injections, only patients with a PRE-SIAQ and at least one POST-SIAQ will be considered. There is no formal method for comparing PRE-SIAQ and POST-SIAQ; only some items are common to the PRE-SIAQ and the POST-SIAQ. For the common items, a histogram will display the scores by domain before the first self-injection and after the injection at Weeks 4, 8, 12, 24, 48, 72 and 96.

Seven items are common between the PRE-SIAQ and the POST-SIAQ. They are grouped into 3 domains (see [Appendix B](#) for further details) which will be compared:

- Feeling about injection including 3 items.
- Self-confidence including 3 items.
- Satisfaction with Self-injection including 1 item in common.

See [Appendix B](#) for further details about the scoring of each domain of the PRE-SIAQ and of the POST-SIAQ.

These analyses will be performed overall.

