### **10.1.2 Open-label Treatment Period**

#### **10.1.2.1 Inclusion visit (Visit 3 / Week 0 / Day 1 +3)**

During inclusion visit the below will be performed:

- Assess Inclusion/Exclusion Criteria: confirm eligibility and include the patient.
- Collect AEs.
- Record concomitant medication.
- Review patient's diet. Patient should be on a NCEP-ATPIII TLC diet or equivalent.
- Physical examination.
- Urine pregnancy test (females of childbearing potential only).
- Urinalysis.
- Injection training reminder could be performed at inclusion visit as needed.
- If the patient is confirmed eligible, the Investigator will start the next study procedures:
  - IVRS/IWRS contact for allocation of one 7-digit treatment kit number according to the list for the alirocumab injections. Investigators should never allocate a treatment kit number to a patient without contacting IVRS/IWRS,
  - IMP kit dispensation as per treatment kit number provided by IVRS along with schedule reminder. The patient injection instruction manual and treatment administration package should be provided,

- The first open-label IMP injection will take place at the study site, but only after the assessment of all evaluations planned at that visit. Close supervision, feedback and further training to be provided for IMP administration. The patient should be observed for at least 30 minutes after the injection.
- Ask the patient to complete the SIAQ (post-module).

Reminders:

- An appointment will be given for the next study site visit.
- Remind patient to be in fasting conditions (ie, overnight, at least 10 to 12 hours fast and refrain from smoking) for next study site visit. Also, alcohol consumption within 48 hours and intense physical exercise within 24 hours preceding the next study site visit are discouraged.
- Patient will be provided with a diary and instructed on its completion. Patient will be asked to bring the diary to the next study site visit.
- Patient will be given a sharp container to discard all used pens.

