#### **11.4.5 Analyses of patient's acceptability of self-injection (see [Section 9.2.3](#))**

Analysis of the SIAQ will be conducted on the safety population.

A descriptive summary of total and domain scores will be provided for each visit and change from baseline at Weeks 4, 8, 12, 24, 48, 72 and 96.

Further details will be provided in the SAP.

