## 1 OVERVIEW AND INVESTIGATIONAL PLAN

### 1.1 STUDY DESIGN

This trial is to be conducted as a multi-country, multi-center prospective, single arm, open-label, phase IIIb clinical trial.

After enrollment, patients received study treatment (alirocumab) 150 mg subcutaneous (SC) once every 2 weeks (Q2W) or 75 mg SC Q2W. The dose could be adjusted according to the investigator, based on treatment response.

Alirocumab was administered on top of stable maximally tolerated statin therapy ± other lipid modifying therapy (LMT) over a period of at least 12 weeks and until the product becomes commercially available and reimbursed but for a period not exceeding 30 months of treatment.

In each country, patient recruitment was scheduled to end when alirocumab became commercially available and reimbursed. In this case, study treatment could be switched to the commercial product (or another LMT) once the patient had completed the minimum of 12 weeks of study treatment. As a consequence, the total duration of study depend on countries with a minimum of 12 weeks in each participating country and the number of patients at each time point beyond 12 weeks of study treatment is likely to be very variable.

During the course of the study, the investigator managed, based on his/her own clinical judgment and low density lipoprotein cholesterol (LDL-C) value, adjustment of alirocumab doses (either up-titration from 75 to 150 mg Q2W or down-titration from 150 to 75 mg Q2W, or maintenance of the dose). In case a modification of the current dose was decided, the patient was contacted by the site staff and an unscheduled visit was planned to dispense the new treatment kit and retrieve the current one.

The study consists of:

- A screening period of up to 3 weeks, including a training injection during which the patient or another designated person (such as spouse, relative, etc) was trained to self-inject/inject. An optional dedicated visit could be scheduled as needed.
- An open-label treatment period with alirocumab of at least 12 weeks and until the product becomes commercially available and reimbursed. However, the open label treatment period cannot exceed 30 months.
- An end-of-treatment (EOT)/end-of-study (EOS) visit taking place at least 2 weeks after the last study treatment injection.

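### The PRE/POST SIAQ comparison is not paired by week, so a shift in domain scores can reflect who is left rather than a change in perception

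*SAP*

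**What the plan says.** SAP 2.4.6 offers this comparison as its analysis of how perception changes between the first and later self-injections. It restricts the set ("only patients with a PRE-SIAQ and at least one POST-SIAQ will be considered"), notes that "There is no formal method for comparing PRE-SIAQ and POST-SIAQ", and then, for the items shared by both modules, plans that "a histogram will display the scores by domain before the first self-injection and after the injection at Weeks 4, 8, 12", continuing through Weeks 24, 48, 72 and 96. The shared items form three domains: feelings about injections, self-confidence and satisfaction.

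The POST records that count at a given week are defined just before, under the analysis of the POST module. "If questionnaires were completed while the patient did not self-inject or were not performed the same day of an injection", they are left out. SAP 2.5.3 summarises continuous scales on observed data and promises counts of missing observations.

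Protocol 11.4.5 planned something further: "A descriptive summary of total and domain scores will be provided for each visit and change from baseline at Weeks 4, 8, 12, 24", and on to Week 96. SAP 1.5 lists the changes made to the protocol's statistical section. Its only SIAQ entry concerns the analysis population. SAP 1.6 reports no modifications.

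On Week 0 the documents disagree. The inclusion-visit procedures in Protocol 10.1.2.1 say "Ask the patient to complete the SIAQ (post-module"), and the flow chart in Protocol 1.2 has a SIAQ POST tick at the inclusion visit. Protocol 9.2.3 and SAP 2.1.5 start the POST module at Week 4, and no SAP summary or display includes Week 0.

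**The concern.** The PRE score is taken over a fixed set of patients, while each POST score is taken over whichever part of that set still supplies a usable questionnaire. If the patients who stop contributing differ in their scores from those who continue, the bars move even when no patient has changed their mind. A reader of the histogram cannot separate the two explanations, and without a within-patient change nothing else in SAP 2.4.6 separates them either.

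Acceptability of self-injection throughout the study is one of the two secondary objectives (Protocol 5.2, SAP 1.2.2), and this display is the SAP's only analysis of change in it.

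**Working it through.** The plan has no figure to reproduce here. It gives no SIAQ sample size, standard deviation, expected score or attrition rate. The check is therefore a reading of who enters each bar, followed by arithmetic on assumed inputs.

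**1. Who is in each bar**

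| Bar | Patients |
|---|---|
| PRE | Everyone in the comparison set: a PRE and at least one POST, at any week |
| POST at week w | The part of that set with a questionnaire at week w, completed on the day of a self-injection |

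A patient whose only usable POST is at Week 4 stays in the PRE bar and the Week 4 bar and is in no later bar.

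**2. Ways of dropping out of later bars**

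- Stopping self-injection. Protocol 8.1.1 allows a trained designated person to inject, and Protocol 9.2.3 limits the SIAQ to patients who inject themselves. This route can be related to the score being measured. The documents give no rate or reasons for it.
- Leaving the study. SAP 1.1 ties treatment length to availability and reimbursement in each country and expects that "the number of patients at each time point beyond 12 weeks of study treatment is likely to be very variable". This route need not be related to the score, although a changing country mix could move the mean up or down.
- Not answering, or answering on a day without an injection.

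**3. Size when no patient changes**

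Let q be the share of the comparison set without a usable POST at that week, S the mean PRE score of those present and L that of those missing.

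- PRE bar = (1 − q)S + qL
- POST bar with zero change = S
- Apparent shift = S − [(1 − q)S + qL] = q(S − L)

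Items run from 1 (worst) to 5 (best). With assumed q and assumed gaps S − L:

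| q | gap 0 | gap 0.5 | gap 1.0 |
|---|---|---|---|
| 10% | 0 | 0.05 | 0.10 |
| 20% | 0 | 0.10 | 0.20 |
| 40% | 0 | 0.20 | 0.40 |
| 60% | 0 | 0.30 | 0.60 |

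If those who remain scored lower at PRE than those missing, the same figures apply with a minus sign.

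**4. Check by simulation**

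PRE scores were drawn as normal with mean 3.8 and SD 0.8, cut to 1–5, with zero true change (all assumed). Over q from 10% to 60%, a correlation between score and staying of 0.2 gave shifts of 0.03 to 0.15, a correlation of 0.5 gave 0.08 to 0.36, and a correlation of 0 gave 0.00.

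**5. The paired version**

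Setting each week's POST against the PRE of the same patients gave 0.00 in every one of these zero-change scenarios.

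**6. Week 0**

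The conflict has a practical consequence. Whether a patient whose only POST is at Week 0 meets the entry condition is not stated. If so, that patient enters the PRE bar and no POST bar.

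**The case against.** The analyses are descriptive, with no tests (SAP 2.4). The objective is only to document acceptability, SAP 2.5.3 will show missing counts, and SAP 1.1 openly expects variable numbers after Week 12. Protocol 11.4.5 left details to the SAP, and the SAP gives a reason for a limited comparison: only some items are common to both modules. The SAP is silent on pairing rather than against it, and Appendix B, to which it refers for scoring, cannot be read in the available text.

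Much of this stands, and it limits the consequence. It does not close the gap. Missing counts show the bars shrinking, but they do not align the PRE bar with the patients who remain, and they do not separate patients who stopped self-injecting from patients who left. The seven common items are enough for a paired change in three domains.

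Four stronger readings are tempting and are not supported:

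- That the PRE bar holds all patients. It does not. Patients with no POST at all are excluded from it.
- That the display must inflate acceptability. That needs leaving to be related to low scores. Reimbursement-driven leaving need not be, and the shift can go either way.
- That the effect is large. Suppose leavers are fixed at 2.5 against an overall mean of 3.5. Then (3.5 − 2.5p)/(1 − p) gives remaining means of 3.61, 3.75 and 3.93, hence shifts of 0.11, 0.25 and 0.43, at p = 10%, 20% and 30%. But that assumes gaps of 1.11, 1.25 and 1.43 points, growing with drop-out, and nothing in the documents supports them.
- That the SAP throws away a complete Week 0 POST data set. Collection at Week 0 is contradicted within the protocol, and the flow chart's columns are not cleanly legible in the available text. Protocol 8.1.2 lets a designated person give the first injection, and SAP 2.4.1 tabulates who gave it, so not every later self-injector would have a valid Week 0 questionnaire.

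**Conclusion.** The point holds in a limited form. Followed as written, SAP 2.4.6 sets one PRE score for a fixed set of patients beside POST scores from a changing part of that set. It does not carry forward the protocol's change from baseline, and the SAP's own list of changes does not say so. A shift in a domain score could therefore be a composition effect, of unknown sign.

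Its size rests on two quantities that the documents do not give. For 10–20% missing at a week and a gap of 0.5–1.0 point, it is 0.05 to 0.20 points on a five-point scale. It grows with more attrition and vanishes if leaving is unrelated to score. No formal decision depends on the display, so this concerns the interpretability of a secondary objective. It is still more than missing detail, because a better analysis was already planned in the protocol.

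**What to change.** In SAP 2.4.6, for the common items of the three shared domains, report at each week the PRE and POST scores of the same patients (those with both) and the within-patient change. Under each week give the number contributing, the number on treatment and the number still self-injecting. If change from baseline is to be dropped instead, declare it in SAP 1.5 with the reason.

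Reconcile Protocol 1.2 and 10.1.2.1 (POST at the inclusion visit) with Protocol 9.2.3 and SAP 2.1.5 (POST from Week 4). Where Week 0 POST data were collected, include Week 0 as the first POST time point, limited to patients who self-injected at that visit, and state whether a Week 0 questionnaire alone satisfies the entry condition.

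The cost is SAP wording and one reprogrammed display, with no new data collection. Pairing removes the composition artefact, but it does not show how patients without a questionnaire at that week would have scored, and the report should say so.
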